Medical condition or disease under investigation	Neurocognitive decline after RT in adult primary brain tumour patients
Purpose of clinical trial	Develop NTCP model to predict neurocognitive function after radiotherapy in brain and base of skull tumours
Primary objective	Develop an NTCP model for neurocognition after RT
Secondary objective (s)	 Estimate prevalence and severity of neurocognitive decline for all cognitive domains Identify brain structures or functional brain areas important in neurocognitive decline (based on dedicated MRI). Search for dose-dependencies of specific neurocognitive skills after RT in adult brain tumour patients Evaluate correlations between RT dosimetry and early brain changes (MRI)
Trial Design	Multicenter observational cohort study

Participating centers	- UZ Gent - Iridium Kankernetwerk Antwerpen
	Primary endpoints:
	 Measure the prevalence and severity of neurocognitive decline compared to baseline at 1 year post-baseline, for all cognitive domains
Endpoints	 Predict neurocognitive dysfunction based on RT dosimetric and other explanatory variables
	Secondary endpoints:
	 Identify early and late changes on structural and functional MR images
	 Evaluate associations with neurocognitive functioning and RT dosimetry
Sample Size	n=120
Summary of eligibility criteria	Adults (≥18 years) with a primary brain or base of skull tumour, who are amenable for conventionally fractionated radiotherapy (photon or proton irradiation)
Maximum duration of treatment of a Subject	Follow-up for at least 2 years after radiotherapy
Version and date of final protocol	Version 2, 15-06-2022
Version and date of protocol amendments	/

2. Background and rationale

The worldwide incidence rate of primary malignant brain and other central nervous system (CNS) tumours in 2018 was 3.5 per 100,000, representing an overall total of 296,851 individuals¹. Due to improved treatment strategies, long-term survival can be achieved in an increasing number of CNS patients. Limiting side-effects and safeguarding quality of life after treatment is therefore of utmost importance. Treatment modality of primary brain tumours depends both on the histologic, molecular and genetic characteristics of the tumour but mostly consists of multimodal therapy including surgery, radiotherapy (RT) and/or chemotherapy. One of the most elusive long-term toxicities related to RT of the brain is neurocognitive decline². Deterioration in neurocognitive functioning, including memory loss, concentration disorders, decline in executive, visuospatial and language functioning, places a heavy burden on both the medical and socio-economic aspects of the patients' lives³. We observe such a decline in up to half of all these patients treated with RT⁴. Predicting which patients will experience more or less cognitive sequelae is still a challenge.

Preclinical studies have shown that radiation-induced brain injury is due to microstructural modifications at both hippocampal- and non-hippocampal-dependent brain regions⁵. While the exact pathophysiology is complex and poorly understood, the dose delivered to specific (sub)structures is known to correlate with neurocognitive decline⁵⁻⁷. For instance, hippocampal dosimetry was associated with memory decline⁸, while higher RT dose to frontal areas was associated with a decline in executive functioning such as verbal fluency⁹. However, these findings have not been validated prospectively yet. Despite such increased risk, RT-induced neurocognitive decline and its impact on adult survivors is poorly studied and many knowledge gaps have to be filled. Previous research on long-term neurocognitive outcomes¹⁰⁻¹². This is partly due to the lack of a standardized neurocognitive follow-up. Even though international guidelines suggested a standard battery for non-CNS cancer patients¹³, study designs remain inconsistent, and the sensitivity and specificity of this battery in CNS patients remain inconclusive. Moreover, empirical studies on treating or preventing cognitive impairment in patients with brain tumours have failed to show significant results¹⁴⁻¹⁵.

Recently developed imaging techniques provide not only an opportunity to estimate and visualise RT-induced damage, but they also offer the opportunity to identify new targets for interventions to prevent or lessen cognitive side-effects. Previous neuroimaging studies only focused on micro-, and macrostructural anatomical changes after RT, including grey¹⁶ and white matter¹⁷ (WM) changes. More recent advanced magnetic resonance imaging (MRI) acquisition and analysis techniques, including diffusion-weighted and functional MRI, are nowadays available. They allow us to probe the underlying structural and functional brain network (i.e. "connectome"), respectively. These techniques might be more sensitive to detect possible therapy-induced structural and functional changes in the brain topology, which could relate to cognitive deficits. Furthermore, cognitive impairment may be driven by damage to specific fibre tracts associated with cognitive assessments, which can be modelled based on diffusion-weighted MRI tractography¹⁸.

The proposed observational cohort study will combine the above-mentioned MR imaging techniques together with elaborate neuropsychological assessments and RT dosimetry in 120

patients who will be examined baseline (before RT) and followed longitudinally after RT. By doing so, we hope to uncover vulnerable brain regions and detect early imaging changes to identify patients at risk. Since neurotoxicity is a complex multifactorial process, the best way to combine these data and make predictions about RT-induced effects is to build so-called normal tissue complication probability (NTCP) models. These mathematical models allow us to estimate the risk of a particular side effect in a structured and validated way for every individual patient. This will enable us to simulate the patient's toxicity risks to spare neurocognitive function in daily life. A previous effect has been conducted by Gondi in 2012, but included a limited number of patients and this model has not been validated to date¹⁹.

In this exploratory prospective study, we thus aim to provide the clinical, radiological and dosimetric data to build a validated NTCP model for neurocognitive decline, which is currently lacking.

3. Trial objectives and Design

3.1 Trial objectives

The aim of this trial is to study the long-term impact of multimodal treatment (chemotherapy, radiotherapy and surgery) in adult brain and base of skull tumours on neurocognitive functioning using neuropsychological testing combined with advanced MR imaging techniques in a multicenter observational cohort study. We differentiate two main objectives.

The first objective is to build an NTCP model for neurocognitive decline after RT (for each cognitive domain separately), linking dose-volume parameters to structures within the brain susceptible to neurological damage and neurocognitive decline after radiotherapy. These NTCP models will be used to make predictions on neurocognitive decline in future primary brain tumour patients receiving cranial RT. It will provide us with a much needed, evidence-based tool to select the optimal treatment modality for each individual patient and enables us to tailor cranial irradiation towards neurocognition-sparing treatment in the future.

The second objective is to evaluate dose-dependent neurocognitive decline. In particular, we will investigate:

- Prevalence and severity of neurocognitive decline after RT for all cognitive domains
- Brain structures or functional brain connections important in neurocognitive functioning (based on dedicated MRI).
- Dose-dependencies of specific neurocognitive skills after RT in adult brain tumour patients
- Correlations between RT dosimetry and early brain changes (MRI)

With this prospective observational trial, we aim to map the neurocognitive side effects of the irradiation treatment in cranially irradiated patients and the clinical and dosimetrical factors that play a role. Based on these findings, we plan to set up future prospective trials to validate these findings.

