3.4 Trial Design

This is an observational cohort study which evaluates primary brain tumour patients longitudinally at the following timepoints: baseline (minimal 4 weeks after surgery (if indicated), before radiotherapy), three months (+/- 2 weeks) after end of radiotherapy, 1 year after end of radiotherapy (+/- 1 month) and 2 years after end of radiotherapy (+/- 1 month). At each visit, neurocognitive testing, a self-report inventory and/or advanced MR imaging will take place. During and after radiotherapy and at each follow-up visit, adverse events will be monitored using CTCAEv5.0²⁰.

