5.1 By visit

Each patient will have 5 trial visits. The sequence of procedures to be performed at each visit is detailed below.

		SCREENI							END
		NGS PHASE	FOLLO	V-UP	PHASE				OF STUDY
Visit name	Protocol	Screenings visit	Baseline visit*	RT start	End of RT	3 months after	1 year after RT	2 years after RT	End of study visit°
Day				DO	Dstop	3 M	12 M	24M	24 M
Visit window	3.4	D-28 to 0	D -21 to 0		+/- 3D	+/- 2 W	+/- 4 W	+/- 4W	+/- 8W
Informed consent	IC	x							
Eligibility criteria assessment	4	x							
Patient information and history ^a	R	x							
Tumour characteristics ^a	R	x							
RT charachteristics ^a	R				x				
Questionnaires ^b	5.3		x				х	х	
Neurocognitive testing ^c	5.2		x				x	x	
MRI ^d	5.4		x			х	х		
RT plan ^d					x				
CRF toxicity ^a	6.2			x	х				х

End of study	R					х
assessment						

*: minimally 4 weeks after surgery

IC: informed consent form

R: REDCap

o: after 2 years or at progression

a: in REDCap (by CTA or MD)

b: in REDCap (online survey, filled in by patient via REDCap platform)

c: in REDCap (by neuropsychologist)

d: to upload coded DICOM images and RT plan in OncoPlace (by CTA)

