5.2 Neurocognitive assessment

We will perform a standardized neurocognitive test battery in all patients at baseline (prior to RT) and each consecutive year (1 year and 2 years post-RT). The acquisition of neurocognitive assessments takes approximately 1 hour. Results will be followed over time and compared to normative data ^{21,22}.

All these tests and questionnaires have been extensively described and used to quantify neurocognitive functioning in adults. Both neurocognitive testing and completion of the questionnaires takes place in the hospital.

We will use a broad evaluation of neurocognitive performance.

- The Montreal Cognitive Assessment (MOCA), is a screening instrument for cognitive deficits in multiple domains²³.
- Trail Making Task (TMT)²⁴, is an executive task which requires to link characters and digits in the correct sequence.
- Digit span (subtest of the Wechsler Adult Intelligence Scale(WAIS))²⁵ is a working memory task, which requires to repeat digits in same, reversed and sequencing order.
- The Hopkins Verbal Learning Test- Revised (HVLT-R)²⁶ is a verbal memory task for which participants need to repeat 12 words (three repetitions of free-recall) to assess verbal learning. Afterwards, they are asked to repeat or recognize the memorized words (Delayed recall and recognition).
- Controlled Word Association Test (COWAT)²⁷ assesses categoric and phonemic fluency. The participant is required to make verbal associations to a category or different letters of the alphabet by saying all the words which they can think of in this category or beginning with a given letter.
- The Stroop Color and Word Test (SCWT)²⁸ assesses the ability to inhibit cognitive interference that occurs when the processing of a specific stimulus feature impedes the simultaneous processing of a second stimulus attribute.
- The digit symbol substitution test of the WAIS (coding)²⁹ measures processing speed. This test consists of digit-symbol pairs followed by a list of digits. Under each digit the subject

should write down the corresponding symbol as fast as possible. The number of correct symbols within the allowed time is measured.

Cognitive domain	Neurocognitive test	Outcome measurement time				
Attention	TMT B					
Memory	HVLT immediate recall	Sum score - learning				
	HVLT delayed recall	Sum score				
	HVLT recognition	Good recognition-mistakes				
	WAIS IV digit span forward	Total number of series				
Executive functioning	COWAT	Sum of words				

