7.1 Sample size

Study subjects will be recruited from the radiation-oncology center of three centers: UZ Leuven, UZ Gent and Iridium Kankernetwerk Antwerpen. From a pragmatic perspective, we estimate to recruit 12-15 patients yearly in each of the three centers, resulting in 120 patients in three years in total.

Cognitive impairment has been reported in primary brain tumour patients and is roughly estimated to be present in about half of patients³⁹⁻⁴⁰. Although limited (good quality) evidence exists for our

type of study, power calculations were performed based on the two most extreme studies (i.e. one showing minimal amount of cognitive impairment⁴¹ and one showing maximal amount of cognitive impairment⁴². In both studies cognitive performance is assessed at baseline and about 12 months after radiotherapy in primary brain tumours. In the study by Moretti et al⁴², we used the cognitive outcome results of patients 9-12 months after radiotherapy (45-60 Gy), since the studied population will receive radiotherapy doses within this range. For power calculations, we used the performance on the digit span forward (processing speed) since the prevalence of impairment on this test was low (<20%). Based on these studies, effect sizes of d= 0,368 and d= 1,271 were found with a power of 0,800 and 0,868 respectively. This power would be 0,979 and 1,000 in our specific explorative study, in case of 120 inclusions. In order to detect this difference after 12 months with a power of 0.800 and a two-sided significance level α =0,05, the total required sample size would thus range between 8-60 patients. Power calculations were performed using Gpower 3.1⁴³.

Sample size calculation for the prediction models was performed using a recently developed software package⁴⁴. Since the event rate of cognitive impairment is unclear, we performed power calculations for the lowest and highest event rate, i.e. 0,2-0,5 (see above). When considering 4 candidate predictors and rMSPE of 0,1, the required sample sizes ranges between 90 and 120 patients respectively. Therefore, including 120 patients will allow building a sufficiently complex prediction model combining four dosimetric and/or clinical features.

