7.2.1 Neuropsychological data

The following research questions are addressed by using multiple statistical tests.

- 1. How severe is the neurocognitive decline after treatment and how does it change over time?
- 2. Which neurocognitive domains are affected in which patients?

The first question is addressed by investigating the neurocognitive performance of primary brain and base of skull tumour patients. The performance on neurocognitive measures of the patients will be assessed at 3 timepoints over time. The raw test-scores are converted to normalized zscores based on normative data for each cognitive test. For each cognitive test, cognitive impairment is defined as a z-score \leq 1.5, and patients will be dichotomized according to their impairment status (impaired versus unimpaired). The frequency of impairment will be reported as descriptive information.

We will assess the evolution in the z-scores with a mixed repeated measures model to test changes throughout time. However, if the data are not normally distributed, the Friedman test will be used as alternative approach. The effects of the patient- and treatment-related predictors on the neuropsychological and questionnaire scores will be investigated using general linear models (predictors= tumour location, radiation dose, covariates= gender, age at treatment, time since treatment and socio-economic status) at each timepoint. Bonferroni correction will be applied as

method for statistical correction of multiple tests, for each test outcome (n=5 outcomes; memory, executive functioning, attention, visuomotor function, working memory) that is predicted.

Effect sizes of the tests will be reported. Partial eta squared (hp2) will be computed to estimate effect sizes (weak effect: $np^2 \approx 0.03$; moderate: $np^2 \approx 0.06$; large: $np^2 \geq 0.14$) for linear relationships between predictor and each outcome (e.g. age, time since treatment). Cohen's d will be used to estimate effect sizes for subgroup differences (small effect: 0.2 < d < 0.3; medium: 0.3 < d < 0.8; large: d > 0.8).

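### The aim in 3.1 includes the impact of surgery, but cognitive testing of operated patients starts only after surgery, and the covariates listed in 7.2.1 include neither surgery nor the interval from surgery to baseline

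*Protocol*

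**What the plan says.** The general aim in Protocol section 3.1 is to "study the long-term impact of multimodal treatment (chemotherapy, radiotherapy and surgery) in adult brain and base of skull tumours on neurocognitive functioning". The two objectives beneath it are narrower: "The first objective is to build an NTCP model for neurocognitive decline after RT (for each cognitive domain separately") and "The second objective is to evaluate dose-dependent neurocognitive decline".

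Section 3.4 places the first assessment at "baseline (minimal 4 weeks after surgery (if indicated), before radiotherapy"), and the visit table in 5.1 repeats "minimally 4 weeks after surgery". Section 5 has patients screened after biopsy or surgery, or on referral to the radiotherapy centre. Section 5.2 schedules cognitive testing "at baseline (prior to RT) and each consecutive year (1 year and 2 years post-RT"). No pre-operative test is planned. The second primary endpoint in 3.2 is decline at one year relative to this baseline.

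Surgery appears in the first primary endpoint in 3.2, among the therapy variables that may explain decline in the NTCP models. For change over time, 7.2.1 says: "We will assess the evolution in the z-scores with a mixed repeated measures model to test changes throughout time". That sentence lists no covariates. The general linear models described next use tumour location and radiation dose as predictors. Their covariates are gender, age at treatment, time since treatment and socio-economic status.

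**The concern.** A stated aim should be answerable from the planned measurements. Here one of the three named treatments has already been given when measurement begins, so the change from baseline cannot show what it did.

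The second issue is attribution. The primary change runs from a post-operative state to one year after radiotherapy. If cognition is still changing after surgery at baseline, that change is counted together with the effect of radiotherapy. Patients can enter at different distances from surgery, so the contribution may differ between them. The covariates the protocol does list would not separate it.

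At stake are a conclusion about surgery that the design cannot deliver, and a one-year change read as a radiotherapy effect when part of it may belong to something else.

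**Working it through.** **1. What the change score contains.** For an operated patient, let P be the pre-operative score and s the effect of surgery already present at baseline. Let c be any further post-operative change between baseline and one year, and r the change from radiotherapy, chemotherapy and all other causes over the same period.

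- Baseline = P + s
- One year = P + s + c + r
- Change = (P + s + c + r) − (P + s) = c + r

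The term s cancels, and P is never observed. No within-patient contrast among baseline, 1 year and 2 years recovers s. The term c stays in the change and is not separable from r without further information.

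**2. What a between-patient comparison gives.** The words on surgery being indicated in 3.4 imply that some patients may have none.

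- Operated minus unoperated at baseline = s + (difference in P between the groups)
- Operated minus unoperated in change = c + (difference in r between the groups)

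Both bracketed differences depend on tumour type, location and the reason for operating or not. The comparison is possible but confounded. Z-scores against norms describe status after all treatment and do not separate its components.

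**3. Whether the interval is bounded.** Sections 3.4 and 5.1 set a minimum of 4 weeks from surgery. The baseline window in 5.1, day −21 to day 0, is counted from the start of radiotherapy, not from surgery. No upper limit on the interval from surgery is stated, so c may vary between patients.

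**4. Whether a listed covariate captures it.** The list in 7.2.1 has no surgery term. Its time-since-treatment covariate does not say which treatment. If it is counted from radiotherapy, it is nearly constant at a given visit (within 1 month at 1 and 2 years, by 3.4) and says nothing about the interval before baseline. The NTCP candidates in 7.2.4 include treatment modality and time since treatment, but not time since surgery.

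**5. Whether 7.1 is affected.** Inputs from 7.1: d = 0.368 and 1.271, two-sided α = 0.05, N = 120. For a paired t-test the noncentrality is d√n on n − 1 degrees of freedom.

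| d | n | d√n | Power | Stated in 7.1 |
|---|---|---|---|---|
| 0.368 | 60 | 2.85 | 0.801 | 0.800 |
| 0.368 | 120 | 4.03 | 0.979 | 0.979 |
| 1.271 | 8 | 3.59 | 0.867 | 0.868 |
| 1.271 | 120 | 13.92 | 1.000 | 1.000 |

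The protocol's statement, "This power would be 0,979 and 1,000 in our specific explorative study, in case of 120 inclusions", reproduces. According to 7.1, both source studies tested at baseline and about 12 months after radiotherapy. Each d is therefore an observed change over that period, not a pure radiotherapy effect.

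**The case against.** The strongest reply is that the sentence in 3.1 describes multimodal treatment collectively, while everything operative concerns radiotherapy: both objectives, the primary endpoint on decline and the closing paragraph of 3.1. For those, a pre-radiotherapy baseline is the right reference. This stands, and it is why the remedy for the aim is rewording and not a new visit.

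It can also be said that surgery is not ignored, since 3.2 names it, 7.2.4 has treatment modality as a candidate and section 11 collects it. That stands for the NTCP models. It does not reach the models of change in 7.2.1, and nowhere is the surgery-to-baseline interval listed.

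Thirdly, the mixed-model sentence gives no covariates at all, and its details may be left to a statistical analysis plan. That is fair, and silence there is not counted as an exclusion. The point rests on the list that 7.2.1 does give.

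A reader might infer that post-operative recovery does offset the radiotherapy decline and that power at 120 patients is lower than stated. The documents do not support this. They give no share of operated patients and no size or direction for cognitive change after week 4. The 4-week minimum already keeps testing out of the immediate post-operative period. Recovery would mask decline, but late effects of surgery would exaggerate it. If the baseline of the study behind d = 0.368 was also post-operative, any recovery is already inside that figure and subtracting it would count it twice. The protocol does not show which kind of baseline it was.

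**Conclusion.** The concern holds as a mismatch between aim and design and as an open question of attribution. It follows from the visit schedule alone that a within-patient effect of surgery cannot be estimated; only a confounded comparison between patients remains. To say that surgery cannot be studied in any way would go too far.

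Residual post-operative change may enter the one-year change. Its size and direction are unknown, and no figure for bias or lost power can be derived from the protocol. The sample size calculation in 7.1 is correct on its own terms and needs no change. The conclusion assumes only that some patients are operated before baseline and that their intervals from surgery differ; the protocol allows both.

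**What to change.** In 3.1, restate the aim as change after radiotherapy, with or without chemotherapy, from the post-operative, pre-radiotherapy state. Name surgery as a covariate, not as an effect to be measured.

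In the 7.2.1 models of change, add surgery (yes/no) and weeks from surgery to baseline, each by visit. Centre the weeks among operated patients and set them to zero for unoperated patients, so that both terms can be fitted together. Report the adjusted change beside the overall change as a sensitivity analysis. The Friedman alternative takes no covariates, so specify this analysis for the mixed model. State also which treatment the time-since-treatment covariate is counted from.

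The cost is one reworded sentence and a few degrees of freedom. With three cognitive visits, each term needs one main effect and two visit contrasts, so 2 × 3 = 6 parameters per outcome. The estimate in unoperated patients will be imprecise and should be presented as such. The surgery date must already be known to apply the 4-week rule, so it need only be kept in the study database. No visit or clinical rule changes.
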